2.2 Secondary Objectives

- **2.2.1** To determine whether cabozantinib can significantly improve overall survival (OS) compared to placebo in patients with advanced pancreatic NET whose disease has progressed after prior therapy.
- **2.2.2** To determine whether cabozantinib can significantly improve overall survival (OS) compared to placebo in patients with advanced carcinoid tumors whose disease has progressed after prior therapy.
- **2.2.3** To evaluate safety and tolerability of cabozantinib versus placebo in patients with advanced pancreatic NET using CTCAE and PRO-CTCAE.
- **2.2.4** To evaluate safety and tolerability of cabozantinib versus placebo in patients with advanced carcinoid tumors using CTCAE and PRO-CTCAE.
- 2.2.5 To evaluate the overall radiographic response rate of cabozantinib versus placebo in patients with advanced pancreatic NET whose disease has progressed after prior therapy.
- **2.2.6** To evaluate the overall radiographic response rate of cabozantinib versus placebo in patients with advanced carcinoid tumors whose disease has progressed after prior therapy.

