5.0 STUDY CALENDAR

The pre-study testing intervals are guidelines only. Laboratory and clinical parameters during treatment are to be followed using individual institutional guidelines and the best clinical judgment of the responsible physician. It is expected that patients on this study will be cared for by oncology providers experienced in the treatment and supportive care of patients on this trial.

Pre-Study Testing Intervals:

To be completed ≤ 14 DAYS before registration: All laboratory studies, history and physical To be completed ≤ 28 DAYS before registration: Any X-ray or scan of any type which is utilized for tumor measurement per protocol

**Calendar should be followed for both blinded therapy and for cross over patients. Crossover patients WILL NOT complete the Quality of Life and Pharmacokentic substudies. Re-registration should occur \le 28 days of local determination of disease progression while receiving blinded therapy with central confirmation of progressive disease.

	Prior to Registration*	Day 1 of each cycle*	Day 15 of Cycles 1 and 2 (+/- 3 days)	At progression or cessation of protocol treatment**
Tests & Observations				
History and Physical, PS	X	X	X	X
Pulse, BP, Height, Weight	X(1)	X(1)	X(1)	
ECG	X	A		
Adverse Event Assessment – CTCAE	X	X	X	В
Adverse Event Assessment – PRO-CTCAE	X(2)	X(2)		X(2)
Patient Medication Diary		X(3)		
Registration Fatigue/Uniscale Assessment	X(4)			
Laboratory Studies			***************************************	.
CBC w/ Differential, Platelets	X	X	X	
PT/INR, PTT	X			
Serum Creatinine	X	X	X	
Albumin, ALT, AST, Alk. Phos., Bilirubin	X	X	X	
Electrolytes (incl. Ca, Cl, CO2, K, Na, Mg, P), Glucose	X	X	X	
TSH	X	С		
Serum or Urine HCG	X(5)			
Urine Protein and Creatinine	X	D		
Serum Chromogranin A	X	С		
Hormone Assessment	Е	Е		
Staging				
CT Chest/Abd/Pelvis (or equiv.)	F	F		F
Real-time Central Review				X(6)
For patients who consent to pa	rticipate in A0216	б 02-НО1, А021 602	2-PP1, and A02160	02 Biobanking:
Quality of Life Substudy ⁷	0	•	(+/- 1 week) (i.e. nticancer therapy;	

Pharmacokinetic Substudy ⁷	Submission of plasma specimens on Day 1 of Cycles 1, 2, and 3 and on Day 15 of Cycles 1 and 2; see Section 6.2 , Section 14.2 .
	Submission of specimens within 28 days of registration, Cycle 1 Day 1, Cycle 2 Day 1, and at the time of progression; see Section 6.2

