- * Labs completed prior to registration may be used for Day 1 of Cycle 1 tests if obtained ≤ 14 days prior to treatment. For subsequent cycles, all labs, scans, tests, and observations may be obtained +/- 3 days of scheduled clinic visit. Labs completed prior to re-registration must be completed ≤ 28 days.
- ** If protocol therapy is discontinued for reasons other than disease progression, physical examination, performance status, and radiologic imaging studies should be performed every 12 weeks (+/- 1 week) until disease progression or start of new anticancer therapy, whichever comes first. Patients who discontinue study treatment due to disease progression (or who start a new anticancer therapy after discontinuing study treatment for reasons other than disease progression) should be followed every 6 months for survival until 8 years after registration. See Section 12.0.
- Height only collected at baseline; weight only measured at baseline, on Day 1 of Cycles 1, 2, and 3, and on Day 15 of Cycles 1 and 2.
- Patients complete PRO-CTCAE by paper booklet ordered through the CTSU website. See Section 4.3 and Section 4.7 for ordering instructions. See Section 9.1 for administration instructions. See Appendix I for PRO-CTCAE assessments for IRB submission and review only. PRO-CTCAE booklets should be administered at the following time points: ≤ 21 days prior to treatment, Day 1 of every cycle, and at the time of progression (or cessation of protocol treatment). PRO-CTCAE should not be collected after patients crossover.
- The diary must begin the day the patient starts taking the medication and must be completed per protocol and returned to the treating institution (or compliance must be documented in the medical record by any member of the care team). See Appendix II.
- 4 To be completed after registration but ≤ 21 days prior to treatment.
- 5 For women of childbearing potential, see Section 3.2.6; must be done ≤ 14 days prior to registration and reregistration.
- Restaging scan documenting progressive disease while on blinded therapy must be submitted for real-time central review within 24 hours of local determination; see Section 6.3 and Section 7.2.2 for instructions regarding imaging submission and IROC notification of cases when there is a local determination of progressive disease and request for real-time central review.
- 7. Crossover patients will not participate in the Quality of Life or the Pharmacokentic substudies.

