9.1.2 Solicited Adverse Events

The following adverse events are considered "expected" and their presence/absence should be solicited, and severity graded, at baseline and for each cycle of treatment by CTCAE, PRO-CTCAE, or both (with the exception of Day 15 of Cycles 1 and 2 for CTCAE).

CTCAE v5.0 Term	PRO-CTCAE v1.0 Term	CTCAE v5.0 System Organ Class (SOC)	
Neutrophil count decreased		Investigations	
Platelet count decreased		Investigations	
Alanine aminotransferase increased		Investigations	
Aspartate aminotransferase increased		Investigations	
Palmar-plantar erythrodysesthesia syndrome	Hand-foot syndrome (a rash of the hands or feet that can cause cracking, peeling, redness, or pain)	Skin and subcutaneous tissue disorders	
Rash maculo-papular	Rash	Skin and subcutaneous tissue disorders	
Hyperglycemia		Metabolism and nutrition disorders	
Hypothyroidism		Endocrine disorders	
Hypertension		Vascular disorders	
Fatigue	Fatigue, tiredness, or lack of energy	General disorders and administration site conditions	
Diarrhea	Loose or watery stools (diarrhea)	Gastrointestinal disorders	
Mucositis oral	Mouth or throat sores	Gastrointestinal disorders	
	Problems with tasting food or drink	Gastrointestinal disorders	
	Decreased appetite	Gastrointestinal disorders	
	Nausea	Gastrointestinal disorders	

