9.2 CTCAE Routine Reporting Requirements

In addition to the solicited adverse events listed in Section 9.1, the following table outlines the combinations of time points, grades and attributions of AEs that require routine reporting to the Alliance Statistics and Data Management Center. Questions about routine reporting should be directed to the Data Manager.

NOTE: PRO-CTCAE data should not be used for determining attribution, dose modifications, or reporting of serious adverse events.

Combinations of CTCAE Grade & Attribution Required for Routine AE Data Submission on Case Report Forms (CRFs)

Attribution	Grade 1	Grade 2	Grade 3	Grade 4	Grade 5
Unrelated		a	a	a	a
Unlikely		a	a	a	a
Possible		a, b	a, b	a, b	a, b
Probable		a, b	a, b	a, b	a, b
Definite		a, b	a, b	a, b	a, b

- Adverse Events: Other CRF Applies to AEs occurring between registration and within 30 days of the patient's last treatment date, or as part of the Clinical Follow-Up Phase.
- b) Adverse Events: Late CRF Applies to AEs occurring greater than 30 days after the patient's last treatment date.

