INJUINT, FUISONING P		Wound complication	
		vvouriu complication	
INVESTIGATIONS	Alanine aminotransferase	T	Alamina aminatyanafayaa
	increased		Alanine aminotransferase increased (Gr 3)
	Aspartate aminotransferase		Aspartate aminotransferase
	increased		increased (Gr 3)
	Lipase increased		Lipase increased (Gr 4)
	Platelet count decreased		Platelet count decreased (Gr 3)
Weight loss			Weight loss (Gr 3)
METABOLISM AND NU	ITRITION DISORDERS		
Anorexia			Anorexia (Gr 3)
	Dehydration		
	Hypocalcemia		
	Hypokalemia		
	Hypomagnesemia		
	Hypophosphatemia		
MUSCULOSKELETAL /	AND CONNECTIVE TISSUE	DISORDERS	
	Arthralgia		
	Generalized muscle		
	weakness		
	Muscle cramp		
	 	Osteonecrosis of jaw	
NEDVOUG OVOTEL	Pain in extremity		
NERVOUS SYSTEM DI			
	Dizziness		
Dysgeusia	 		Dysgeusia (Gr 2)
	Headache	later and in the	
		Intracranial hemorrhage	
		Ischemia cerebrovascular	
		Reversible posterior leukoencephalopathy syndrome	
		Stroke	

Adverse Events with Possible Relationship to XL184 (Cabozantinib) (CTCAE 5.0 Term) [n= 3219]			Specific Protocol Exceptions to Expedited Reporting (SPEER)
Likely (>20%)	Less Likely (<=20%)	Rare but Serious (<3%)	
		Transient ischemic attacks	
RENAL AND URINARY D	ISORDERS		
	Hematuria		
		Proteinuria	
RESPIRATORY, THORAG			
	Cough		
	Dyspnea		
		Pneumothorax ⁶	
		Respiratory fistula ⁷	
	Respiratory hemorrhage ⁸		
	Voice alteration		Voice alteration (Gr 3)
SKIN AND SUBCUTANEO	OUS TISSUE DISORDERS	S	
	Alopecia		
	Dry skin		Dry skin (Gr 2)
	Hair color changes		Hair color changes (Gr 1)
Palmar-plantar erythrodysesthesia syndrome			Palmar-plantar erythrodysesthesia syndrome (Gr 3)
	Rash maculo-papular		Rash maculo-papular (Gr 3)
VASCULAR DISORDERS			
Hypertension			Hypertension (Gr 3)
	Thromboembolic event ⁹		

¹This table will be updated as the toxicity profile of the agent is revised. Updates will be distributed to all Principal Investigators at the time of revision. The current version can be obtained by contacting Your name, the name of the investigator, the protocol and the agent should be included in the e-mail.

²Gastrointestinal fistula includes Anal fistula, Colonic fistula, Duodenal fistula, Esophageal fistula, Enterovesical fistula, Gastric fistula, Gastrointestinal fistula, Ileal fistula, Jejunal fistula, Oral cavity fistula, Pancreatic fistula, Rectal fistula, and Salivary gland fistula under the GASTROINTESTINAL DISORDERS SOC.

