13.3.2 Secondary Endpoints

For both cohorts: overall survival, adverse events, and radiographic response rate.

Overall Survival (OS)

The secondary endpoint of this study is overall survival, defined as the time from randomization to death, from any cause. Patients who do not have an OS event will be censored for OS at the date they were last known to be alive.

Adverse Events (AEs)

CTCAE AEs and the maximum grade for each type of AE will be recorded for each patient. Similarly, scores (0-4) and the maximum score for each PRO-CTCAE item will be recorded for each patient.

Radiographic Response Rate

A secondary endpoint of this study is (confirmed) radiographic response rate, defined as the proportion of patients in each arm whose best response is either complete response (CR) or partial response (PR) prior to crossover.

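### No weight is required after Cycle 3 Day 1, so ascertainment of later weight loss, a likely cabozantinib toxicity, depends on site practice

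*Combined protocol and SAP*

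**What the plan says.** The calendar in Section 5.0 has a row for "Pulse, BP, Height, Weight", marked before registration, on Day 1 of each cycle and on Day 15 of Cycles 1 and 2, and blank at progression or cessation. Every mark carries footnote 1, which limits height to baseline and adds "weight only measured at baseline, on Day 1 of Cycles 1, 2, and 3, and on Day 15 of Cycles 1 and 2". The same calendar applies to patients who cross over.

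Other provisions bear on whether weight loss would still be captured later:

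- Section 7.1: treatment continues until progression, unacceptable toxicity or withdrawal of consent.
- Section 9.4: weight loss is in the likely (>20%) column of the cabozantinib risk list, which is based on 3219 patients.
- Section 9.1.2: for the solicited events, "their presence/absence should be solicited, and severity graded, at baseline and for each cycle of treatment". Weight loss is not among them.
- Section 9.2: a table sets out the "grades and attributions of AEs that require routine reporting to the Alliance Statistics and Data Management Center". For non-solicited events this starts at grade 2, whatever the attribution, up to 30 days after last treatment.
- Section 5.0, opening text: "Laboratory and clinical parameters during treatment are to be followed using individual institutional guidelines and the best clinical judgment of the responsible physician".
- Section 13.3.2: "CTCAE AEs and the maximum grade for each type of AE will be recorded for each patient". Safety and tolerability by CTCAE is a secondary objective in both cohorts (Section 2.2).

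**The concern.** The size of a weight loss can be established only by comparing a current weight with an earlier one. For a drug given until progression, the plan requires weights for the first two cycles and the first day of the third, and none after that. Weight loss is a listed likely toxicity but is not solicited, so no form prompts the site to look for it. A site that weighs patients routinely will detect and grade it; a site that does not may miss it or grade it from impression.

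At stake is even ascertainment of one adverse event within a secondary endpoint. The endpoint takes each patient's maximum grade over the whole treatment period, and Section 13.5.3 compares adverse event rates between arms with a chi-square or Fisher's exact test. If capture after the second month varies by site, the reported maximum grade may be too low, and the arm with longer exposure has more unscheduled time in which that can happen.

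**Working it through.** **1. Where the weight schedule fits.** The on-treatment weight dates are Cycle 1 Days 1 and 15, Cycle 2 Days 1 and 15, and Cycle 3 Day 1. These are exactly the five PK sampling dates in Section 5.0, and Section 14.2.4 names weight as a PK covariate. The schedule serves the PK substudy. The documents give no safety reason for ending it there.

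**2. Timing of the last required weight.** Cycles last 28 days (Section 7.1), so Cycle 3 Day 1 comes 2 × 28 = 56 days after the first dose, or 56 / 30.4375 = 1.84 months.

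**3. Inputs and model.** Section 13.2 assumes exponential survival, with median PFS of 8.8 months on cabozantinib (n = 124) and 5 months on placebo (n = 61) in pancreatic NET, and 12 months (n = 141) and 7 months (n = 69) in carcinoid. The share progression-free at time t is S(t) = 0.5^(t / median).

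**4. Check of the model against the plan's own figures.** Section 14.1.4 expects 138 of 185 and 169 of 210 patients to be progression-free at 12 weeks. At t = 3.0 months:

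- Pancreatic: 124 × 0.5^(3/8.8) + 61 × 0.5^(3/5) = 97.9 + 40.2 = 138.1.
- Carcinoid: 141 × 0.5^(3/12) + 69 × 0.5^(3/7) = 118.6 + 51.3 = 169.8 (the unrounded terms give 169.8).

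Both agree with the plan to within one patient.

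**5. Still progression-free at the last required weight (t = 1.84 months).**

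- Pancreatic, cabozantinib: 0.5^(1.84/8.8) = 86.5%, about 107 of 124.
- Pancreatic, placebo: 0.5^(1.84/5) = 77.5%, about 47 of 61.
- Carcinoid, cabozantinib: 0.5^(1.84/12) = 89.9%, about 127 of 141.
- Carcinoid, placebo: 0.5^(1.84/7) = 83.3%, about 58 of 69.

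In cycles, the assumed cabozantinib medians are 8.8 × 30.4375 / 28 = 9.6 and 12 × 30.4375 / 28 = 13.0. Required weights stop at the start of the third.

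**6. Allowing for stops before progression.** Patients also stop for toxicity or withdrawal, so PFS overstates time on drug. The documents give no expected time on treatment. As an assumption, take an exponential median of 3, 4 or 6 months: the share still on treatment at Cycle 3 Day 1 is 0.5^(1.84/3) = 65%, 0.5^(1.84/4) = 73% or 0.5^(1.84/6) = 81%. Under the exponential model the same percentages give the share of expected treatment time that lies after the last required weight.

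**7. Whether another provision supplies the weight.**

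- History, physical and CTCAE assessment continue on Day 1 of every cycle, but none of these entries requires a weight.
- The grade 2 reporting rule obliges a site to report what it has found. It does not make the site measure.
- PRO-CTCAE asks about appetite, not weight, and is not collected after crossover.
- GI.NET21 item 45 asks whether weight loss has been a problem. It is patient-rated, asked every 12 weeks, and belongs to an optional substudy that excludes crossover patients.
- The enhanced central monitoring of treatment in Section 13.6 covers the first two cycles.

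None of these yields a measured weight after Cycle 3 Day 1.

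**The case against.** The strongest reply is that the footnote is deliberate and that later weight loss is already covered. History, physical, performance status and CTCAE assessment take place every cycle. Non-solicited events of grade 2 or higher must be reported whatever their cause, including those within 30 days of stopping. Both arms follow the same blinded schedule, and many sites will weigh patients anyway. Weight loss is not a named endpoint or a named analysis.

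Much of this stands, and it rules out four stronger readings that a reader might infer:

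- *That later weight loss is lost.* It is not. Reporting of grade 2 and above is mandatory; what is missing is the required measurement behind the grade. Grade 1 weight loss is not routinely reported at any time, since non-solicited reporting starts at grade 2.
- *That expedited reporting of severe cases depends on these weights.* The SPEER lists exceptions: an event is expedited only if it exceeds the grade shown. For weight loss that grade is 3, so weight loss through grade 3 is exempt.
- *That the calendar contradicts itself.* The row carries the footnote mark, and the footnote narrows weight just as it narrows height. It qualifies the row.
- *That the trial is shown to under-count weight loss, mostly on cabozantinib.* The documents allow no estimate of missed events. The direction is an inference from longer expected exposure.

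The reply does not supply a weight. Leaving clinical parameters to institutional guidelines is exactly what makes ascertainment uneven.

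**Conclusion.** The point holds as one of uneven ascertainment. After Cycle 3 Day 1, no weight is required for a likely toxicity that is not solicited, so detection and grading of weight loss of grade 2 or higher depend on site practice. Its maximum grade may be under-ascertained, probably more on cabozantinib.

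Under the protocol's PFS assumptions, about 87% (pancreatic NET) and 90% (carcinoid) of cabozantinib patients are progression-free when required weights end, against 78% and 83% on placebo. If median time on treatment is only 3 to 6 months, 65% to 81% are still on drug at that point, so the gap remains large. These figures measure how much treatment lies beyond the last required weight; they do not measure missed events. They rest on exponential times and, for the PFS figures, on treatment running to progression.

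The effect is confined to one adverse event within a secondary safety endpoint. PFS, sample size, power and alpha are unaffected, and expedited reporting is not materially affected. The change is worth making because it is cheap, but the primary conclusion does not depend on it.

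**What to change.** Amend footnote 1 in Section 5.0 so that height stays at baseline only and weight is recorded at baseline, on Day 1 of every cycle, on Day 15 of Cycles 1 and 2, and at cessation of treatment. Mark the cessation column to match, and make sure that the value is entered in Rave. The existing PK weight dates are all retained.

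The cost is one extra measurement and one data field per visit. Patients already attend on Day 1 of every cycle for pulse and blood pressure, and history and physical are already marked at progression or cessation. The forms are not part of the documents, so whether a weight field already exists for later cycles cannot be checked here. This changes data collection only; no dose or treatment rule is altered.

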6.0 DATA AND SPECIMEN SUBMISSION

6.1 Data Collection and Submission

Medidata Rave is a clinical data management system being used for data collection for this trial/study. Access to the trial in Rave is controlled through the CTEP-IAM system and role assignments.

Requirements to access Rave via iMedidata:

- A valid CTEP-IAM account: and
- Assigned a Rave role on the LPO or PO roster at the enrolling site of: Rave CRA, Rave Read Only, Rave CRA (Lab Admin), Rave SLA, or Rave Investigator.

Rave role requirements:

- Rave CRA or Rave CRA (Lab Admin) role must have a minimum of an Associate Plus (AP) registration type;
- Rave Investigator role must be registered as an Non-Physician Investigator (NPIVR) or Investigator (IVR); and
- Rave Read Only role must have at a minimum an Associates (A) registration type.

Refer to for registration types and documentation required.

This study has a Delegation of Tasks Log (DTL). Therefore, those requiring write access to Rave must also be assigned the appropriate Rave tasks on the DTL.

Upon initial site registration approval for the study in Regulatory Support System (RSS), all persons with Rave roles assigned on the appropriate roster will be sent a study invitation e-mail from iMedidata. To accept the invitation, site staff must either click on the link in the email or login to iMedidata via the CTSU members' website under *Data Management* > *Rave Home*, and click to *accept* the invitation in the Tasks pane located in the upper right-corner of the iMedidata screen. Site staff will not be able to access the study in Rave until all required Medidata and study specific trainings are completed. Trainings will be in the form of electronic learnings (eLearnings) and can be accessed by clicking on the eLearning link in the *Tasks* pane located in the upper right corner of the iMedidata screen. If an eLearning is required for the study and has not yet been taken, the link to the eLearning will appear under the study name in the *Studies* pane located in the center of the iMedidatascreen; once the successful completion of the eLearning has been recorded, access to the study in Rave will be granted, and a *Rave EDC* link will replace the eLearning link under the study name.

Site staff that have not previously activated their iMedidata/Rave account at the time of initial site registration approval for the study in RSS will receive a separate invitation from iMedidata

to activate their account. Account activation instructions are located on the CTSU website in the Data Management section under the Rave resource materials (Medidata Account Activation and Study Invitation Acceptance). Additional information on iMedidata/Rave is available on the CTSU members' website in the Data Management > Rave section at by contacting the CTSU Help Desk at

Data Quality Portal

The Data Quality Portal (DQP) provides a central location for site staff to manage unanswered queries and form delinquencies, monitor data quality and timeliness, generate reports, and review metrics.

The DQP is located on the CTSU members' website under Data Management. The Rave Home section displays a table providing summary counts of Total Delinquencies and Total Queries. DQP Queries, DQP Delinquent Forms, DQP Form Status and the DQP Reports modules are available to access details and reports of unanswered queries, delinquent forms, forms with current status, and timeliness reports. Review the DQP modules on a regular basis to manage specified queries and delinquent forms.

The DQP is accessible by site staff that are rostered to a site and have access to the CTSU website. Staff that have Rave study access can access the Rave study data using a direct link on the DQP.

To learn more about DQP use and access, click on the Help icon displayed on the Rave Home, DQP Queries, DQP Delinquent Forms, DQP Form Status and DQP Reports modules.

Data Submission Schedule

A Data Submission Schedule is available on the Alliance study webpage within the Case Report Forms section. The Data Submission Schedule is also available on the CTSU website within the study-specific folders.

Patient-completed Booklets

Patient-completed questionnaire booklets for this study are to be ordered prior to the registration of any patients (see Section 4.3). Samples of questionnaire booklets are available in Appendix I for reference and IRB submission only. They are not to be used for patient completion. Booklets must be given to patients to complete and patients should be instructed to return the booklets to site staff in person, and site staff will enter patient responses into Rave.

Note: There are two mandatory quality of life items included in the main study: Registration Fatigue/Uniscale and PRO-CTCAE Adverse Event Assessments; see Section 4.3 for booklet ordering instructions, Section 5.0 and Section 9.1 for administration instructions, and Appendix I for examples of the assessments for IRB submission and review. There are two additional quality of life items included as part of the optional A021602-HO1 substudy: EORTC Tools and Global Impression of Change Assessments; see Section 4.3 for booklet ordering instructions, Section 5.0 and Section 14.1 for administration instructions, and Appendix I for examples of the assessments for IRB submission and review.

